#### 7.4.6. Clinical Safety Laboratory Assessments

[Table 13](#) outlines the clinical laboratory tests that will be conducted during this study. Blood and urine specimens will be collected using applicable safety precautions and will be processed according to the central clinical laboratory's instructions. Urinalysis will be evaluated at the study center using supplies provided by Revance or designee.

**Table 13:** **Clinical Laboratory Tests**

[figure not shown]
Serum Chemistry	Hematology	Urinalysis	Additional Tests
Glucose	Hemoglobin	Specific gravity	Prothrombin time (PT) (screening only)
Total bilirubin	Hematocrit	pH	UPT (WOCBP only)*
Alanine aminotransferase	Leukocyte Count (total)	Glucose	
Aspartate aminotransferase	Leukocyte Count (differential)	Protein	
Alkaline phosphatase	Red Blood Cell Count	Blood	
Blood urea nitrogen	Platelet Count	Bilirubin	
		Ketones	

\*If positive at timepoints after study treatment, confirm by serum pregnancy test

It is the investigator's responsibility to review the results of all laboratory tests as they become available. For each laboratory test result outside the reference range, the investigator must ascertain if the abnormal lab result is a clinically significant result for that individual subject. Likewise, if laboratory tests are taken at follow-up visits, the investigator must ascertain if this is an abnormal and clinically significant change from pretreatment for that individual subject. The investigator may repeat the laboratory test or request additional tests to verify the results of the original laboratory test.

The investigator must sign and date all written laboratory results (e.g., urinalysis, hematology, chemistry, PT, and pregnancy tests) and note Not Clinically Significant or Clinically Significant

for each out of range laboratory value. If a laboratory value is determined to be a clinically significant result for that subject, this will be considered an AE.

## 8. Statistical Considerations

### 8.1. Sample Size Determination

A sample size of 48 is selected

### 8.2. Populations for Analyses

For purposes of analysis, the following populations are defined.

Population	Description
Enrolled	All subjects who signed ICF, confirmed eligible and received treatment
Evaluable	All enrolled subjects who receive treatment and have any post treatment assessment of IGA-FWS at maximum frown
Safety	All enrolled subjects who receive at least 1 treatment (injection)

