**Endpoints:**

Key Endpoints

- The proportion of subjects achieving a score of 0 (none) or 1 (mild) in GL severity at maximum contraction at Week 4 as assessed by the IGA-FWS
- The proportion of subjects achieving a score of 0 (none) or 1 (mild) in FHL severity at maximum contraction at Week 4 as assessed by the IGA-FHWS
- The proportion of subjects achieving a score of 0 (none) or 1 (mild) in LCL severity at maximum contraction at Week 4 as assessed by the IGA-LCWS

Safety Evaluations:

- Vital signs
- Physical examination
- [REDACTED]
- Injection site evaluation
- Concomitant therapies/medications
- Clinical laboratory tests (hematology, serum chemistry, prothrombin time [PT], urinalysis)
- [REDACTED]
- Adverse events (AEs)
- Incidence, severity, and relationship to study drug of treatment-emergent AEs (TEAEs) and serious adverse events (SAEs) during the overall study duration.

Evaluations:

- FACE-Q™
  - FACE-Q™ Appraisal of Lines: Overall
  - FACE-Q™ Appraisal of Lines: Forehead
  - FACE-Q™ Appraisal of Lines: Between Eyebrows
  - FACE-Q™ Appraisal of Lines: Crow's Feet Lines
  - FACE-Q™ Satisfaction with Forehead and Eyebrows
  - FACE-Q™ Psychological Function
  - FACE-Q™ Satisfaction with Outcome
- Facial Age Self Evaluation (FASE)
- Global Aesthetic Improvement Scale (GAIS-Subject and Investigator)
- Subject Global Satisfaction with Treatment
- Patient Naturalness Assessment (PNA)
- Photography of treatment areas including standardized image capture of right, left, and frontal views at rest and at maximum contraction (frown, smile, and forehead elevation); and standardized video capture of frontal and oblique views at maximum contraction (frown, smile, and forehead elevation).

**Study Population:** Approximately 48 male and female subjects aged 18 and over years of age.

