## 4. Study Population

Approximately 48 female or male subjects, 18 of age and older with moderate to severe GL, FHL, and LCL at maximum contraction will be enrolled. Subjects must meet all the inclusion criteria and none of the exclusion criteria to be eligible for the study.

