#### **8.3.1. Efficacy Analyses**

In general, descriptive summaries will include means, standard deviations, median, lower and upper quartiles, and ranges for continuous variables; and counts and proportions for categorical measures. Kaplan-Meier curves will be plotted for each time-to-event endpoint and median duration with associated 95% CIs will be provided. Proportion of subjects with response at a given time point will be reported based on observed cases, as well as based on proportion of treated subjects. As this is an open-label study with no placebo comparator arm, no formal hypothesis tests are planned.

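### The Safety set inherits an eligibility condition from Enrolled, so as worded it can leave out a subject who was injected

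*Protocol*

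**What the plan says.** Section 8.2 of the protocol defines three analysis populations:

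- The **Enrolled** set combines consent, eligibility and treatment: "All subjects who signed ICF, confirmed eligible and received treatment".
- The **Evaluable** set starts from Enrolled and adds a glabellar rating after treatment; its definition reads "All enrolled subjects who receive treatment and have any post treatment assessment of IGA-FWS at maximum frown".
- The **Safety** set also starts from Enrolled, in these words: "All enrolled subjects who receive at least 1 treatment (injection)".

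Section 4 gives the meaning of eligibility: "Subjects must meet all the inclusion criteria and none of the exclusion criteria to be eligible for the study".

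Section 8.3.2 undertakes to summarise all treatment-emergent adverse events that are reported and to list any serious ones by subject. It sets no eligibility condition. The primary objective (Sections 1.1 and 3) covers efficacy and safety together.

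For efficacy, the Synopsis lists one key endpoint per region, each on its own investigator scale. Section 8.3.1 gives two denominators for response, the observed cases and everyone treated: "Proportion of subjects with response at a given time point will be reported based on observed cases, as well as based on proportion of treated". Section 8.3 leaves to the SAP, which was not available for this review, the choice of population for each analysis.

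**The concern.** A safety population should be defined by exposure. Here it is a subset of Enrolled, and Enrolled depends on eligibility. Section 4.5 foresees significant deviations through accident or mistake, so treatment of a subject who should not have been treated is a case the protocol itself contemplates.

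Such a subject need not be typical. One exclusion criterion (Section 4.2, item 2) concerns frontalis activity that masks lid or brow ptosis, and ptosis is one of the events the Introduction reports for combined treatment with another toxin. If a subject injected despite such a criterion were outside Safety, the set could lose the person most likely to have an event. At stake is the safety half of the primary objective, in a study small enough for one subject to change the reported rate.

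A lesser matter is that Evaluable depends on one of the three investigator scales, although the study treats three regions and has a key endpoint for each.

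**Working it through.** **1. Set logic.** Let C be consent signed, K confirmed eligible and T treated, reading treatment as any injection.

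- Enrolled = C ∩ K ∩ T
- Safety = Enrolled ∩ (at least one injection) = C ∩ K ∩ T = Enrolled

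The injection clause removes nobody. Among consented, treated subjects, K is the only condition that can remove anyone.

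**2. Who can drop out.** The protocol does not say whether K means the site's confirmation before dosing or eligibility that is in fact established.

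| Injected subject | K = site confirmation before dosing | K = eligibility in fact |
|---|---|---|
| Confirmed and eligible | in Safety | in Safety |
| Confirmed, later found ineligible | in Safety | out |
| Ineligible and never confirmed | out | out |

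At least one kind of exposed subject is outside Safety on either reading.

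**3. Size.** The protocol gives no safety rate or precision target to reproduce. The only document figure used is the sample size of 48 (Section 8.1). Numbers of excluded subjects and events below are assumptions.

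*No events.* The upper two-sided 95% exact limit is 1 − 0.025^(1/n).

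| Excluded (assumed) | n | Upper limit |
|---|---|---|
| 0 | 48 | 7.40% |
| 1 | 47 | 7.55% |
| 2 | 46 | 7.71% |
| 3 | 45 | 7.87% |

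*The excluded subject has an event* (exact Clopper–Pearson intervals).

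- One event in all: 1/48 = 2.08% (0.05% to 11.07%) becomes 0/47 = 0% (0% to 7.55%).
- Two events in all: 2/48 = 4.17% (0.51% to 14.25%) becomes 1/47 = 2.13% (0.05% to 11.29%).

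For scale, the Introduction quotes eyelid and brow ptosis rates of 0.6% to 1.9% for another toxin. If rates of that order applied here, which is an assumption, the expected count of each would be 48 × 0.006 = 0.29 to 48 × 0.019 = 0.91, less than one case. A single excluded subject could then be the only case.

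**4. Evaluable.** Membership requires that subjects "have any post treatment assessment of IGA-FWS at maximum frown". Two of the three key endpoints are on other scales: "The proportion of subjects achieving a score of 0 (none) or 1 (mild) in FHL severity at maximum contraction at Week 4", on the IGA-FHWS, and "The proportion of subjects achieving a score of 0 (none) or 1 (mild) in LCL severity at maximum contraction at Week 4", on the IGA-LCWS. A subject with forehead and canthal ratings but no frown rating would be out; one with a frown rating only would be in. But any one post-treatment frown rating qualifies, Section 3.4 plans 10 on-site follow-up visits (Weeks 2, 4, 8, 12, 16, 20, 24, 28, 32 and 36), and all three regions are to be rated. Either mismatch would be rare.

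**The case against.** The strongest reply is that confirmed eligibility naturally means the site's check before dosing. Eligibility is reviewed at screening (Section 7.2.1, item 2) and again on Day 1 before the product is given (Section 7.2.2, item 2). A subject who passed both checks, was injected and later proved ineligible was still confirmed eligible and stays in Safety. Only a subject injected with no confirmation would be lost, which should be rare. This stands as a limit on the point. It does not remove it, because the text does not settle the reading and some exposed subjects are excluded on both.

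A second reply is that Section 8.3.2 has no eligibility limit and the SAP assigns populations to analyses. A reader might infer that events in ineligible subjects would disappear from the report. The protocol does not say so: reported events are to be summarised and serious ones listed. What stands is that a set named Safety is defined in a way that does not match that intention. Deferral to the SAP does not cure this, because the definition itself is given in the protocol.

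A third reply concerns Evaluable. A reader might infer that forehead and canthal responses get the wrong denominator. No section makes Evaluable the denominator for those regions. Section 8.3.1 names observed cases and treated subjects, and observed cases are naturally counted scale by scale. This reply largely succeeds.

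It is also fair to say that the move from 1/48 to 0/47 is a constructed worst case, and that no test or decision rule depends on it, since no hypothesis test is planned.

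**Conclusion.** The Safety definition should be corrected. By its own wording it equals Enrolled, carries an eligibility condition and can exclude an exposed subject, which fits neither the safety reporting in Section 8.3.2 nor the primary objective. This is something the protocol states badly, not detail left for the SAP.

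The size depends on conduct. The effect is nil if no ineligible or unconfirmed subject is treated. With no events, each excluded subject moves the upper limit by about 0.15 to 0.16 percentage points. The reported rate changes visibly only if an excluded subject has an event, as in the assumed change from 2.1% to 0%. It would go too far to say that every treated subject found ineligible is certainly dropped, since that depends on a reading the protocol leaves open.

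The Evaluable wording is a minor point. It matters only if the set is used for forehead or lateral canthal lines, which the protocol does not state, and its practical effect is probably small.

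**What to change.** In Section 8.2, define Safety as *all subjects who receive any injection of DAXI, regardless of eligibility*. This removes the dependence on Enrolled and on how confirmation of eligibility is read.

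If Evaluable is to be used for forehead or lateral canthal lines, define it per region: any post-treatment assessment at maximum contraction on that region's investigator scale.

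The cost is rewording one table row, or two with Evaluable, and keeping the SAP consistent. No additional subjects, data or procedures are needed. The change should be made before database lock.

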### **8.3. Statistical Analyses**

The statistical analysis plan will be developed and finalized before database lock and will describe the detailed methods of analysis, the subject populations to be included in the analyses, and procedures for accounting for missing, unused, and spurious data. This section is a summary of the planned statistical analyses of the efficacy and safety endpoints.

#### **8.3.1. Efficacy Analyses**

In general, descriptive summaries will include means, standard deviations, median, lower and upper quartiles, and ranges for continuous variables; and counts and proportions for categorical measures. Kaplan-Meier curves will be plotted for each time-to-event endpoint and median duration with associated 95% CIs will be provided. Proportion of subjects with response at a given time point will be reported based on observed cases, as well as based on proportion of treated subjects. As this is an open-label study with no placebo comparator arm, no formal hypothesis tests are planned.

#### **8.3.2. Safety Analyses**

Adverse events (AEs) occurring during the study will be recorded and classified according to MedDRA terminology. Those occurred one or after treatment are considered as treatment emergent. All reported TEAEs will be summarized, in terms of the number of subjects reporting events, system organ class, preferred term, severity, relationship to study drug, outcome, action taken and seriousness. For summarization of event causality and seriousness, subjects will be counted only once within a system organ class or preferred term using the event with the event with the greatest relationship for causality and the event with the highest severity. A summary of TEAEs leading to discontinuation will also be provided.

A by-subject listing of any SAEs will be provided and all SAEs will be summarized by severity and relationship to study treatment.

Clinical laboratory test and vital sign results will be summarized by visit and if applicable a shift table will be used to evaluate the shift in status from baseline at each visit. [REDACTED]

[REDACTED] Physical examination, injection site findings, [REDACTED] will be summarized as described in the SAP.

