### 7.4.1. Adverse Events and Serious Adverse Events

#### 7.4.1.1. Evaluation of Adverse Events and Serious Adverse Events

For this protocol, an **adverse event (AE)** is any untoward medical occurrence (e.g., sign, symptom, disease, syndrome, intercurrent illness, clinically significant abnormal laboratory finding, injury or accident) that emerges or worsens following administration of investigational product and until the end of study participation that may not necessarily have a causal relationship to the administration of the investigational product. An AE can therefore be any unfavorable and/or unintended sign (including a clinically significant abnormal laboratory result), symptom, or disease temporally associated with the use of an investigational product, whether or not considered related to the investigational product. A treatment-emergent AE is one that occurs after any period of exposure to treatment.

Pre-existing conditions, which increase in frequency or severity or a change in nature as a consequence of an investigational product use will also be considered an adverse event.

An unexpected AE is an adverse reaction, the nature or severity of which is not consistent with the applicable product information (e.g., Investigator's Brochure for an unapproved investigational product or package insert/summary of product characteristics for an approved product).

Any change in the study safety evaluations, (e.g., vital signs, injection site evaluation) post-treatment determined to be clinically significant by the investigator must be reported as an AE.

An **SAE** is any untoward medical occurrence that results in any of the following outcomes:

- Death

- Life-threatening, (i.e., the subject was, in the opinion of the Investigator, at immediate risk of death from the event as it occurred. It does not apply to an AE that hypothetically might have caused death if it were more severe)
- Persistent or significant disability/incapacity or substantial disruption of the subject's ability to carry out normal life functions
- Requires in-patient hospitalization or prolongs hospitalization (i.e., a prolonged hospitalization beyond the expected length of stay; hospitalizations for elective medical/surgical procedures, scheduled treatments, or routine check-ups are not SAEs by this criterion)

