- Congenital anomaly/birth defect (i.e., an adverse outcome in a child or fetus of a subject exposed to the molecule or investigational product before conception or during pregnancy)
- Does not meet any of the above serious criteria but based upon appropriate medical judgement may jeopardize the subject or may require medical or surgical intervention to prevent one of the outcomes listed above (i.e., is a significant or important medical event)

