#### **7.4.1.7. Investigational Product Causality and Severity**

Relationship of an AE to investigational product will be assessed as follows:

- **Definite:** There is a clinically plausible time sequence between the onset of the AE and the administration of investigational product; when the event responds to withdrawal of investigational product and/or recurs with re-administration of investigational product
- **Probable:** There is a clinically plausible time sequence between the onset of the AE and the administration of investigational product; the AE is unlikely to be caused by the concurrent/underlying illness, other drugs or procedures

- **Possible:** There may or may not be a clinically plausible time sequence between the onset of the AE and the administration of investigational product and a cause cannot be ruled out
- **Unrelated:** There is not a temporal or causal relationship to investigational product administration

The investigator is responsible for evaluating all AEs and determining the severity of the event. Severity will be categorized as mild, moderate or severe according to the following definitions:

- **Mild:** Event may be noticeable to subject; does not influence daily activities; usually does not require intervention
- **Moderate:** Event may be of sufficient severity to make subject uncomfortable; performance of daily activities may be influenced; intervention may be needed
- **Severe:** Event may cause severe discomfort; usually interferes with daily activities; subject may not be able to continue in the study; treatment or other intervention usually needed

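### The once-per-subject counting rule for TEAEs in section 8.3.2 confuses seriousness with severity; the effect is minor and one sentence corrects it

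*Protocol*

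**What the plan says.** Protocol section 8.3.2 says that all TEAEs will be summarized by number of subjects and by "system organ class, preferred term, severity, relationship to study drug, outcome, action taken and seriousness". Severity and seriousness are therefore two separate items in that list.

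The next sentence gives the counting rule: "For summarization of event causality and seriousness, subjects will be counted only once within a system organ class or preferred term". The representative events are then named as "the event with the greatest relationship for causality and the event with the highest severity". The words leading into that second part are visibly garbled, with a phrase repeated.

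The definitions stand elsewhere in the protocol:

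- **Seriousness** (7.4.1.1): an SAE "is any untoward medical occurrence that results in any of the following outcomes". The list runs from death to important medical events, the last being one that "may require medical or surgical intervention to prevent one of the outcomes listed above (i.e., is a significant or important medical event".
- **Severity** (7.4.1.7): "Severity will be categorized as mild, moderate or severe according to the following definitions".

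Section 8.3.2 also plans separate SAE output: "A by-subject listing of any SAEs will be provided and all SAEs will be summarized by severity and relationship to study treatment".

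**The concern.** The rule announces one pair of attributes, causality and seriousness, and supplies selectors for another, relationship and severity. Greatest relationship clearly belongs to causality. That leaves highest severity as the only selector available for seriousness, and it is not a valid one. Under the protocol's definitions neither attribute determines the other: an event of moderate intensity that leads to hospitalization is serious, and an event of severe intensity may meet no seriousness criterion.

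At stake is agreement between safety tables. If the sentence is programmed as written, the TEAE-by-seriousness breakdown could show fewer subjects with a serious event in a given SOC or PT than the SAE summary shows. Safety is part of the primary objective, so the counting rule should be unambiguous even though the tables are descriptive.

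**Working it through.** The protocol gives no figure to reproduce here. The check is to apply the sentence as written to the smallest case in which it can go wrong.

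**Inputs.**
- One count per subject within a SOC or PT (8.3.2).
- Selector other than causality: the event of highest severity (8.3.2).
- Severity grades: mild = 1, moderate = 2, severe = 3 (7.4.1.7; the numbers are only labels for the order).
- Seriousness: yes or no by outcome, with no reference to the severity grade (7.4.1.1).

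**Case.** One subject has two TEAEs in the same SOC or PT, one serious with severity *s* and one non-serious with severity *n*. There are 3 × 3 = 9 pairings.

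**Literal reading.** The subject takes the seriousness status of the more severe event.

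| Condition | Pairings (*s*, *n*) | Number | Result |
|---|---|---|---|
| *s* < *n* | (1,2), (1,3), (2,3) | 3 | counted as non-serious: wrong |
| *s* = *n* | (1,1), (2,2), (3,3) | 3 | rule gives no answer |
| *s* > *n* | (2,1), (3,1), (3,2) | 3 | counted as serious: right |

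The total is 3 + 3 + 3 = 9. The pairings are not equally likely in practice, so 3 of 9 is not an error rate. A subject with only one event in the SOC or PT is never misclassified, nor is one whose most severe event there is itself serious.

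**Reading seriousness as a slip for severity.** The sentence becomes the ordinary convention: greatest relationship for causality, highest severity for severity. Nothing is misclassified and the severity table has its rule. The seriousness table then has no stated rule.

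**Any-serious rule.** If a subject counts as serious whenever at least one event in the SOC or PT is serious, all 9 pairings are classified correctly: 0 wrong and 0 unresolved.

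**Scale.** One subject out of 48 is 1/48 = 2.1%, and two are 2/48 = 4.2%. The protocol gives no expected number of SAEs. If one assumes 1 or 2 subjects with an SAE, a single misclassification would move the count in the affected row from 2 to 1 or from 1 to 0. This shows what one misclassified subject would do if it occurred. It does not say how often that would happen.

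**The case against.** **It is a drafting slip, not a chosen method.** The sentence is garbled, and its two selectors are the natural partners of causality and severity. This is probably right. It means that a reader should not conclude that the sponsor decided to assign seriousness from the most severe event; the text never states that link outright. But seriousness is also the last item in the list just before, so a programmer could take the word at face value. On either reading the sentence needs correcting.

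**No serious event can be lost.** This stands. The by-subject listing and the summary of all SAEs are not tied to the once-per-subject sentence. A reader might infer that SAEs would go unreported, and the protocol does not support that. What could differ is one SOC or PT breakdown.

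**The conditions are narrow.** This also stands. A reader might infer that any serious event of low severity is tabulated as non-serious. That happens only when the same subject also has a more severe, non-serious event in the same SOC or PT. At PT level it takes two events coded to the same term. A reader might also infer that half or all of the serious subjects would disappear from the table. That figure assumes 1 or 2 such subjects and then assumes the very coincidence whose frequency is in question, so it does not measure the size of the problem. Because the rule works within a SOC or PT, no effect on an overall count of subjects with serious TEAEs is established.

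**The SAP will settle counting rules.** Section 8.3 calls itself a summary and leaves detailed methods to the SAP, which is not shown. A missing rule would therefore be no finding. Here a rule is stated, and stated wrongly: a SAP that follows it literally takes over the fault, and one that corrects it departs from the protocol's wording.

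**Conclusion.** The concern holds as a minor wording defect. The counting rule in section 8.3.2 is announced for seriousness but selects on severity, which the protocol defines separately. Taken literally, it can count a subject as non-serious in a SOC or PT where that subject had a serious event. It also leaves ties open and gives the severity summary no counting rule.

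The practical effect is small. It requires the literal reading, and a more severe non-serious event alongside the serious one in the same subject and the same SOC or PT. That few such cases will arise in 48 subjects is a judgement, since the protocol gives no event rates. Even then, the consequence is limited to one breakdown that disagrees with the separately planned SAE summary.

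**What to change.** Replace the selection part of the sentence in section 8.3.2 with three separate rules, each applied once per subject within a SOC or PT:

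- for causality, use the event with the greatest relationship;
- for severity, use the event with the highest severity;
- for seriousness, count the subject as serious if any event there is serious.

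If no seriousness table by SOC and PT is intended, it is enough to change the word seriousness to severity in this sentence. The repeated phrase should be removed at the same time.

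The cost is one sentence in the protocol and matching text in the SAP and table specifications. Data collection, visits and treatment do not change.
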